8.6.3. Six-minute Walk Test

The 6MWT is performed at baseline, Month 6, and Month 12/EOT visits.

The 6MWT distance actual, baseline and change-from-baseline will be summarized by visit based on those subjects within the ITT population who have data at that visit. At each visit the baseline summary will reflect those subjects who provided data at that visit.

8.7.1. St. George's Respiratory Questionnaire

The SGRQ is captured at baseline, Month 6, Month 12/EOT, and EOS.

The SGRQ scores (total, symptoms, activities, impacts) actual, baseline and change-from-baseline will be summarized by visit based on those subjects who have data at that visit. At each visit the baseline summary will reflect those subjects who provided data at that visit.

8.7.2. EQ-5D-3L

The EQ-5D-3L is captured at baseline, Month 6, Month 12/EOT, and EOS.

The EQ-5E-3L scores (VAS, Mobility, Self-care, Usual Activities, Pain/Discomfort, and Anxiety/Depression) actual, baseline and change-from-baseline will be summarized by visit based on those subjects who have data at that visit. At each visit the baseline summary will reflect those subjects who provided data at that visit.

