### 3.4 EXPLORATORY ENDPOINTS - EFFICACY

The exploratory endpoints will evaluate the overall population and describe the subjects by treatment arm assigned in the INS-212 study (LAI added to a multi-drug regimen arm and a multi-drug regimen alone).

1. The mean change from Baseline at Month 6 and Month 12/EOT in the overall SGRQ and SGRQ – Part II (Activities of Daily Living)
2. The mean change from Baseline at Month 6 and Month 12/EOT in the EQ-5D-3L
3. Radiological changes in CT scan at EOT, within a sub-set of subjects

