### 7.3.2 EQ-5D-3L

#### 7.3.2.1 Methodology

The EQ-5D-3L, is a preference-based, (multi-attribute) generic health-status classification instrument that generates a composite score reflecting the preference value associated with a given health state. The system has 5 dimensions: mobility, self-care, usual activities, pain/discomfort, and anxiety/depression. Each dimension has 3 levels: no health problems, moderate health problems, and extreme health problems. Current general health is also scored using a visual analog scale.

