#### 7.3.2.2 Assessment

The health state is reported with a 5-digit descriptor ranging from 11111, representing the best case, to 33333, representing the worst case. The score for each domain of the EQ-5D-3L will be reported in the eCRF.

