6. GENERAL CONSIDERATIONS FOR DATA ANALYSES AND HANDLING

6.1. Data Presentation Conventions

Continuous variables will be summarized with means, standard deviations, medians, minimums, and maximums, and, if appropriate, by clinically relevant discretization's. Categorical variables will be summarized by counts and by percentage of subjects in corresponding categories. All data that meaningfully contribute to the objectives of the study will be included. Footnotes will specify the basis for the percentages. For counts of subjects, however, the denominator will generally be the number of subjects in the Safety population and treatment arm (based on treatment assignment in INS-212). All summary tables will be presented by treatment arm. A total summary column may be included in some summary tables wherever relevant.

Summaries of continuous variables that have some values recorded using approximate values (e.g., < or >) will use the numeric part of the value in calculations. Listings will present the data in its original format.

For summaries where rounding is required, rounding will be done to the nearest roundoff unit. For example, if the round-off unit is the ones place (i.e., integers), values $\geq XX.5$ will be rounded up to $XX+1$ while values $< XX.5$ will be rounded down to XX .

Individual subject data obtained from the electronic case report forms (eCRFs), and any derived data will be presented by treatment, site, and subject in data listings.

An unscheduled visit can be used in the determination of baseline values, if it provides the last non-missing value prior to the first dose of the study drug. Post-baseline unscheduled visit data will be presented in the listings only (i.e., unscheduled visit data will not be summarized in tables). If subject has more than one data at a specific visit for any reason, average of the data at that visit will be considered in summary tables.

The analyses described in this plan are considered a priori, in that they have been defined prior to database lock. Any other analyses performed will be considered post-hoc. Posthoc analyses will be labeled as such on the output and identified in the CSR.

All analyses and tabulations will be performed using SAS[®] version 9.4 or higher. Tables, listings, and figures will be created in rich text format.

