The change from baseline (Day 1) in the EQ-5D-3L subject reported health outcomes to all study visits. The EQ-5D-3L consists of two parts. One is a descriptive system of questions and the other an EQ visual analogue scale (EQ-5D-VAS) measurement. The EQ-5D-3L descriptive system is comprised of 5 dimensions: mobility, self-care, usual activities, pain/discomfort and anxiety/depression. For each dimension the response has 3 levels: no problems, some problems, extreme problems. A single index score will be calculated from the response for the 5 dimensions. The index score will be calculated using United Kingdom weights. The algorithm for index value derivation is provided by the EuroQol Group Foundation [1]. The EQ-5D-3L index scores ranges from 0 to 1; 0 meaning death and 1 complete health. The EQ-5D-VAS records the respondent's self-rated health on a vertical, visual analogue scale where the endpoints are labelled 'Best imaginable health state' and 'Worst imaginable health state'. This information will be used as a quantitative measure of health outcome as judged by the subjects.

CT Scan (substudy)

For subjects participating in the CT scan sub-study, CT scan results will be qualified as ‘normal’, ‘abnormal – not clinically significant’ or ‘abnormal – clinically significant’ at baseline and ‘improved’, ‘worsened’ or ‘no change from previous’ at post-baseline assessments. The number and percent of subjects within each CT scan category will be summarized by scheduled visits.

Subject reported symptoms of Nontuberculous Mycobacteria:

The incidence of subjects who reported symptoms of NTM lung infections caused by MAC that are refractory to treatment will be summarized by scheduled visits.

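### The final SAP omits, without explanation, the UK-weighted EQ-5D-3L index and handles five 3-level domains as continuous scores

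*SAP*

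**What the plan says.** The protocol's exploratory endpoint (3.4) is "The mean change from Baseline at Month 6 and Month 12/EOT in the EQ-5D-3L". It does not say which EQ-5D-3L score is meant. Protocol 7.3.2.1 describes an instrument that "generates a composite score reflecting the preference value associated with a given health state", with a visual analogue scale alongside, and states: "Each dimension has 3 levels: no health problems, moderate health problems, and extreme health problems". Protocol 7.3.2.2 reports the health state as a five-digit descriptor and adds: "The score for each domain of the EQ-5D-3L will be reported in the eCRF".

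The SAP for the accelerated submission, section 10.1, says "A single index score will be calculated from the response for the 5 dimensions" and "The index score will be calculated using United Kingdom weights". It also uses the VAS as a quantitative outcome. Its section 11 names the EQ-5D-3L among the efficacy data for which categorical observations get frequencies and shift tables from baseline.

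The final SAP, section 8.7.2, says: "The EQ-5E-3L scores (VAS, Mobility, Self-care, Usual Activities, Pain/Discomfort, and Anxiety/Depression) actual, baseline and change-from-baseline will be summarized by visit" (EQ-5E-3L is a slip for EQ-5D-3L). Its section 6.1 sets this convention: "Categorical variables will be summarized by counts and by percentage of subjects in corresponding categories".

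**The concern.** Two plans for the same study score the same questionnaire differently, and the later one does not say why. The VAS and the descriptive system measure different things: one is the subject's own global rating, the other a profile over five dimensions. An index summarises that profile in one number. Without it, the final analysis describes the profile only through five separate items.

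The way those items are summarised is the second problem. A mean of a 3-level item treats the step from none to moderate as equal to the step from moderate to extreme. It also does not show how many subjects moved in each direction.

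At stake is how well an exploratory quality-of-life result is described, and whether an index at Month 12/EOT could be reported as planned in advance.

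**Working it through.** There is no figure in the plan to reproduce. The index itself cannot be calculated here, because the United Kingdom weights are not in the documents. The check is a comparison of texts, with one small illustration.

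**Step 1: which scores each plan analyses.**

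| | SAP for the accelerated submission | Final SAP |
|---|---|---|
| Index | Yes, UK weights (10.1) | Absent from 7.4, 8.7.2 and the table list in 11.1 |
| VAS | Yes (10.1) | Yes (8.7.2) |
| Five domains | Inputs to the index; frequencies and shifts for categorical efficacy data (11) | Five separate scores with actual, baseline and change (8.7.2) |
| Reason for dropping the index | Not applicable | None given |

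The index is lost and the VAS is common to both. By contrast, the SGRQ, in 8.7.1 of the final SAP, keeps its total score.

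**Step 2: how the final SAP treats the domains.**

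- Baseline: section 7.4 puts the five domains with the VAS, age and 6MWT distance in the group summarised by mean, SD, median and range. The list of variables to be tabulated by category, in the same section, leaves them out. The 6MWT dyspnoea and fatigue scores appear in both lists, so the plan does show distributions for other scores.
- Change: section 8.7.2 specifies actual, baseline and change, and section 11.2 gives that three-block layout to continuously valued parameters. Means of domain change follow from these two sections read together, and from the protocol endpoint being a mean change. No sentence states them outright.
- Convention: a 3-level response is categorical, so section 6.1 calls for counts and percentages.

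**Step 3: status of an index added later.** Section 6.1 of the final SAP classes any analysis not in the plan as post-hoc, to be labelled so on the output and in the CSR. An index at Month 12/EOT falls under that rule.

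**Step 4: what a domain mean can leave out.** Assume, for illustration only, that a share p of subjects improves by one level, the same share worsens by one level, and the rest do not change.

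- Mean change = p × (−1) + p × (+1) = 0
- SD of change = √(2p)

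| p (assumed) | Subjects who changed (2p) | Mean | Median | SD |
|---|---|---|---|---|
| 5% | 10% | 0 | 0 | √0.10 = 0.32 |
| 15% | 30% | 0 | 0 | √0.30 = 0.55 |
| 25% | 50% | 0 | 0 | √0.50 = 0.71 |

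The SD and range show that some subjects moved, but not how many moved each way. Any mean can hide offsetting changes, including the mean change of an index. This step therefore supports counts and shift tables for the domains. It is not an argument for the index.

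**The case against.** The strongest reply is that nothing the protocol names has been lost. The endpoint specifies no score, and protocol 7.3.2.2 speaks of a descriptor and of domain scores, so reporting by domain fits it. This stands. The inconsistency is between the two SAPs, on top of an endpoint that the protocol leaves under-specified. It is not a breach of a named protocol score.

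A reader might infer that the final SAP has no single EQ-5D-3L score whose mean change answers the endpoint, or that it pools the five items into one average. Neither is supported. The VAS is part of the instrument, is a single quantitative score, and is summarised as change at both time points. Each domain is summarised on its own.

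A reader might also infer that EQ-5D-3L results cannot be compared between the two analyses. That goes too far. The VAS is in both plans, the final SAP summarises Month 6 as well as Month 12/EOT, and the responses needed for an index are still collected. Protocol 9.4 does not list the EQ-5D-3L among the first analyses. The SAP for the accelerated submission plans it at Month 6 (2.2.3), but no document shows that a Month 6 index was produced.

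Two further limits stand. The mock-ups are in separate documents, so the actual layout of Table 14.2.5 is unknown and may already show categories. And this is description of an exploratory endpoint with no hypothesis (8.2) and no comparison of prior arms (8.7). What the reply does not remove is the unexplained omission and the explicit use of means for 3-level items at baseline.

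**Conclusion.** The point holds as a minor one. The final SAP leaves out, without a reason, an index that the SAP for the accelerated submission had defined, and it handles five ordinal domains as continuous against its own convention. Two consequences follow. The descriptive system has no composite score in the final analysis, and an index at Month 12/EOT would be post-hoc.

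No error rate, primary safety conclusion or secondary efficacy result is affected. The documents give no basis for a numerical size, and the figures in step 4 rest on assumed shares. The conclusion on domain change rests on reading 8.7.2 with 11.2, and could soften if the mock-ups for Table 14.2.5 show counts by level.

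**What to change.** In final SAP 8.7.2 and Table 14.2.5:

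1. Add the EQ-5D-3L index, with the same United Kingdom weights and algorithm as section 10.1 of the SAP for the accelerated submission, as actual, baseline and change at Month 6 and Month 12/EOT.
2. Keep the VAS as it is.
3. Present each of the five domains as counts and percentages by level, with baseline-to-visit shift tables. Make the matching change to the baseline list in 7.4.

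If leaving the index out was deliberate, say so and give the reason. If the database is already locked, the index can still be derived, but it must carry the post-hoc label.

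The cost is one extra derived variable and a change of table format. No new data are needed, because protocol 7.3.2.2 already has the domain scores recorded.

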8.7.3. Health Care Resource Utilization

Health care resource utilization (HCRU) is a questionnaire based on subject recall asking about the use of hospitalizations, emergency room (ER) visits, doctor visits, and other information. The questionnaire was administered at baseline, Month 1, Month 3, Month 6, Month 9, Month 12/EOT visits.

All summaries of HCRU data will be done by visit.

For subjects who have more than one hospitalization, the duration of hospitalizations for the HCRU summaries is the sum of all hospitalizations durations for the subject. Durations for

unplanned hospitalizations, planned hospitalization, ICU Admissions, hospitalizations due to NTM, and ICU admissions due to NTM will be derived in a similar manner for the summaries.

Hospitalizations

For each hospitalization since the last study visit subjects were asked the following:

- Since your last visit, were you admitted to the hospital?
- Was this a planned hospitalization?
- Dates of admission and release.
- Was the hospital admission related to NTM?
- If you were admitted to the hospital, did it result in being admitted to the ICU?
 - If yes, dates of ICU admission and release.

The number and percentage of subjects within each treatment and total will be presented for the following:

- Since your last visit, were you admitted to the hospital? (yes/no)
- Number of hospitalizations
- Number of unplanned hospitalizations
- Number of planned hospitalizations
- ICU admission (yes/no)
 - Number of ICU admissions
- Admission related to NTM (yes/no)
 - Number of NTM hospitalizations
 - Number of NTM ICU admissions

Summary statistics (n, mean, standard deviation, median, minimum, maximum) will be presented for the following:

- Duration of all hospitalizations
- Duration of unplanned hospitalizations
- Duration of planned hospitalizations
- Duration of ICU admissions
- Duration of hospitalizations due to NTM
- Duration of ICU admissions due to NTM

Emergency Room Visits

For each ER visit subjects were asked the following:

- Since your last visit, did you visit the ER?

- ER Visit Date
- Did your visit to the ER result in being admitted to the hospital?

The number and percentage of subject responses (yes/no) to the questions ‘since your last visit, did you visit the ER’ and ‘did your visit to the ER result in being admitted to the hospital’ will be presented.

Doctor Visits

Regarding doctor visits subjects were asked the following:

- Since your last visit, how many times did you visit a doctor (other than your study related visits)?
- Were doctor's visits related to NTM?
- Reason for Doctor Visits other than NTM

The distribution of the number of times subjects visited the doctor (0, 1, 2, >2) and the question “were doctor's visits related to NTM” (yes/no) will be presented indicating the number and percentage of subjects at each level by treatment and total.

Other

For the ‘other’ subjects were asked the following:

- Are you working?
 - If Yes, how many days did you miss work since your last visit?
 - If Yes, was missed work related to NTM?
- Have you been placed on disability/social security related to you having NTM since your last visit?
- How many hours of sleep (on average) have you been getting since your last visit?
- Have you refrained from certain family/social/work activities based on the symptoms associated with NTM since your last visit?
- Have you added back into your daily routine any previously discontinued activities since your last visit?
 - If Yes, please describe

The number and percentage of subjects within each treatment and total will be presented for the following:

- Response (yes/no) to
 - Placed on disability/social security
 - Refrained from family/social/work activities
 - Added routine activities previously discontinued
 - Working

- If yes, were
 - work days missed
 - work days missed due to NTM
- Distributions of
 - Number of work days missed
 - Number of work days missed due to NTM

Summary statistics (n, mean, standard deviation, median, minimum, maximum) will be presented for the following:

- Average number of hours slept per day
- Number of work days missed
- Number of work days missed due to NTM

8.8. Summary of Reasons for Efficacy Non-Evaluability/Exclusion from Efficacy Analyses

Not applicable

9. SAFETY AND TOLERABILITY

Safety and tolerability summaries will present data for all subjects treated (ie, Safety Population) overall and by the prior INS-212 study treatment the subject received.

The analyses of safety and tolerability data include an overall summary of adverse events (AE), AE preferred terms by body/organ system, drug exposure (duration of treatment), ALIS treatment compliance, concomitant medications, clinical laboratory results, vital signs, , and audiology tests. Adverse events summaries are broken into the 2 groups, treatment-emergent, and post-treatment.

Unless otherwise specified, percentages for all safety tables will be based on the number of subjects in the Safety Population for the total column and treated in the treatment columns.

9.1. Overall Summary of Adverse Events

9.1.1. Overall Summary of Treatment-emergent Adverse Events

The overall summary of AEs will present the number and percentage of subjects meeting the following criteria:

1. At least one TEAE
2. At least one serious TEAE
3. At least one TEAE leading to study drug withdrawn
4. At least one TEAE leading to multi-drug regimen for NTM withdrawn
5. At least one TEAE leading to study drug and MDR multi-drug regimen for NTM withdrawn
6. At least one Serious TEAE leading to study drug withdrawn
7. At least one TEAE leading to death
8. At least one TEAE which is Pulmonary Exacerbation
9. At least one Serious TEAE which is Pulmonary Exacerbation
10. At least one TEAE which is a cough event
11. At least one TEAE related to nebulizer device used for study drug administration
12. Maximum Reported Severity
 - a. Grade 1 (mild)
 - b. Grade 2 (moderate)
 - c. Grade 3 (severe)
 - d. Grade 4 (life threatening)
 - e. Grade 5 (death)
13. Closest Relationship to Study Drug
 - a. Related (Definitely, Possibly, or Probably Related)
 - b. Not related
14. Other suspect therapy
 - a. None
 - b. Azithromycin
 - c. Clarithromycin
 - d. Ethambutol
 - e. Rifampin

- f. Rifabutin
- g. Other

Subjects will be counted only once in Items 1 through 13. Subjects will be counted at the highest severity reported in Item 12. Subjects will be counted at the closest relationship to study drug (ALIS) in Item 13. In Item 14 subjects will be counted only once for each suspect therapy reported; if any suspect therapy is reported, the subject will not be counted in the ‘none’ category.

9.1.2. Overall Summary of Adverse Events Resulting in Hospitalization

For AEs that resulted in hospitalization, the overall summary will present the following information:

- 1. Number and percent
 - a. Of subjects with at least one hospitalization AE
 - b. Number of hospitalizations per subject

9.1.3. Adverse Events of Special Interest

Table 6 lists the adverse events of special interest (AESI) by AESI group, system organ class and preferred term.

Table 6: Adverse Events of Special Interest

AESI Group	System organ class	Preferred term
Neuromuscular	Musculoskeletal and connective tissue disorders	Muscular weakness
	Nervous system disorders	Balance disorder
		Neurotoxicity
		Neuropathy peripheral
		Peripheral sensory neuropathy
Nephrotoxicity	Renal and urinary disorders	Haematuria
		Proteinuria
		Renal failure
		Azotaemia
		Bilirubinuria
		Leukocyturia
		Nitrituria
		Renal impairment
	Investigations	Blood creatinine increased
		Blood urine present
		Creatinine renal clearance increased

AESI Group	System organ class	Preferred term
		Glomerular filtration rate abnormal
		Glomerular filtration rate decreased
		Red blood cells urine positive
		Urine bilirubin increased
		Urinary casts present
Ototoxicity	Ear and labyrinth disorders	Deafness
		Deafness bilateral
		Deafness neurosensory
		Deafness unilateral
		Hearing impaired
		Hypoacusis
		Tinnitus
	Nervous system disorders	Vertigo
		Balance disorder
		Dizziness
		Presyncope
Alveolitis Allergic	Respiratory, thoracic and mediastinal disorders	Alveolitis allergic
		Eosinophilic pneumonia
		Interstitial lung disease
		Pneumonitis
Bronchospasm	Respiratory, thoracic and mediastinal disorders	Asthma
		Bronchial disorder
		Bronchial hyperreactivity
		Bronchospasm
		Dyspnoea
		Dyspnoea exertional
		Prolonged expiration
		Tachypnoea
		Throat tightness
		Wheezing
	Investigations	Forced expiratory volume decreased
		Pulmonary function test decreased
Infective Exacerbation of	Respiratory, thoracic and	Chronic obstructive pulmonary disease

AESI Group	System organ class	Preferred term
Underlying Disease	mediastinal disorders	
	Infections and infestations	Infective exacerbation of bronchiectasis
		Infective exacerbation of chronic obstructive airways disease
		Infective pulmonary exacerbation of cystic fibrosis
		Infective exacerbation of chronic obstructive airways disease
Haemoptysis	Respiratory, thoracic and mediastinal disorders	Haemoptysis
Other Respiratory	Respiratory, thoracic and mediastinal disorders	All preferred terms not mentioned in another group
Exacerbation of COPD	Infections and infestations	Infective exacerbation of chronic obstructive airways disease
	Respiratory, thoracic and mediastinal disorders	Chronic obstructive pulmonary disease

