### **Dose Interruption**

If a subject experiences local respiratory events such as, but not limited to, dysphonia, oropharyngeal pain, and cough while taking LAI that may be distressing to the subject, short interruptions of LAI may be necessary and are permitted. As the frequency of these local respiratory events decreased with continued use in prior LAI studies, it is recommended that LAI is reintroduced after a short interruption of dosing when symptoms subside. Please contact the medical monitor to discuss.

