## 8.3 ADVERSE EVENTS OF SPECIAL INTEREST

Adverse events of special interest (AESI) are those known to be attributed to parenteral amikacin:

- nephrotoxicity, including elevation of serum creatinine, albuminuria, presence of red and white cells, casts, azotemia, and oliguria
- ototoxicity affecting the eighth cranial nerve resulting in hearing loss, loss of balance, or both.
- neuromuscular disorders
- allergic alveolitis
- bronchospasm
- hemoptysis

Cough is often associated with drug products that are nebulized. To properly characterize AEs of cough, specific details regarding AEs of cough will be reported in the AE eCRF pages.

It is expected that subjects in this study will experience a large number of pulmonary exacerbation events due to their underlying lung condition(s). Pulmonary exacerbation will be defined based on the Investigators best clinical judgment. Details of the type of exacerbation should be provided on the AE eCRF.

Protocol Amendment 3.1: 25 May 2017

*This protocol is solely for communicating information about the investigational drug between Inmed Incorporated and study personnel. Information is not to be reproduced, abstracted or used for sharing of information for any other purpose, whatsoever, except with the written permission of Inmed Incorporated.*

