3.2. Study Endpoints

3.2.1. Primary Endpoints

The primary endpoint is the frequency of treatment-emergent adverse events (TEAEs), TEAEs leading to withdrawal from study, treatment-emergent serious adverse events (SAEs), AEs of special interest, clinically significant abnormal laboratory test results, and vital signs measurements. The primary endpoint will evaluate the overall population and describe the subjects by treatment arm assigned in the INS-212 study (ALIS added to a multi-drug regimen arm and a MDR alone).

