9.2.1. Tabulations of Adverse Events

Adverse events will be tabulated presenting the incidence and percentage of subjects along with the number of events by and across prior INS-212 treatment arms. Incidence of an adverse event is the number of subjects reporting the adverse event at least once. The denominator for the percentage is the number of subjects receiving the treatment within the analysis population for the by treatment arm tabulation and total number of subjects enrolled and receiving treatment for the total.

Incidence, percentage, and number of AEs will be reported for subjects reporting at least one AE, within the system/organ class (SOC), and by preferred term within the SOC. Adverse tabulations will be generated for the following:

- Pre-treatment AEs
 - All
 - Serious
 - All
 - Fatal

- Leading to hospitalization
- Treatment-Emergent
 - AEs
 - All
 - Common ($\geq 5\%$)
 - Related to study treatment
 - Leading to withdrawal from study
 - Leading to withdrawal of study treatment
 - Leading to withdrawal of ALIS
 - Leading to withdrawal of MDR
 - Leading to withdrawal of both ALIS and MDR
 - Resulting in study drug interruption
 - Resulting in interruption of ALIS
 - Resulting in interruption of MDR
 - Resulting in interruption of both ALIS and MDR
 - By maximum toxicity grade
 - By relationship to ALIS
 - Related to nebulizer
 - Serious AEs
 - All
 - Common ($\geq 5\%$)
 - Related to study treatment
 - Leading to withdrawal from study
 - Leading to withdrawal of study treatment
 - Leading to withdrawal of ALIS
 - Leading to withdrawal of MDR
 - Leading to withdrawal of both ALIS and MDR
 - Resulting in study drug interruption
 - Resulting in interruption of ALIS
 - Resulting in interruption of MDR
 - Resulting in interruption of both ALIS and MDR
 - By maximum toxicity grade

- By relationship to ALIS
- Resulting in hospitalization
- Related to nebulizer
- Fatal
- AEs of Special Interest
 - All
 - Common ($\geq 5\%$)
 - Related to study treatment
 - Leading to withdrawal from study
 - Leading to withdrawal of study treatment
 - Leading to withdrawal of LAI
 - Leading to withdrawal of MDR
 - Leading to withdrawal of both LAI and MDR
 - Resulting in study drug interruption
 - Resulting in interruption of LAI
 - Resulting in interruption of MDR
 - Resulting in interruption of both LAI and MDR
 - By maximum toxicity grade
 - By relationship to LAI
 - Related to nebulizer
- Serious AEs of Special Interest
 - All
 - Common ($\geq 5\%$)

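### The final SAP's AESI list takes in the whole respiratory SOC, so the any-AESI frequency no longer measures the protocol's six categories, and the SAP text specifies no subject count per AESI group

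*SAP*

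**What the plan says.** Protocol 8.3 opens its list with "Adverse events of special interest (AESI) are those known to be attributed to parenteral amikacin" and bullets six categories: nephrotoxicity, ototoxicity, neuromuscular disorders, allergic alveolitis, bronchospasm and hemoptysis. Cough and pulmonary exacerbation follow the list in the same section, but only to ask for extra detail on the case report form. For cough, "specific details regarding AEs of cough will be reported in the AE eCRF pages".

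Final SAP 3.2.1 makes AESI frequency a component of the primary endpoint, which includes "AEs of special interest, clinically significant abnormal laboratory test results, and vital signs measurements".

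Final SAP 9.1.3 states that "Table 6 lists the adverse events of special interest (AESI) by AESI group, system organ class and preferred term". The table has nine groups. Six correspond to the protocol bullets. The other three are Infective Exacerbation of Underlying Disease, Exacerbation of COPD, and Other Respiratory, the last being "All preferred terms not mentioned in another group" within the respiratory SOC.

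Final SAP 9.2.1 gives one row structure for all adverse event tabulations, the AESI tables included: subjects with any event, then "within the system/organ class (SOC), and by preferred term within the SOC". No AESI-group row is named in 9.1.1, in 9.2.1 or in the table titles of 11.1. SAP 11.2 places the mock-ups in separate documents.

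**The concern.** AESI frequency is meant to isolate a short list of anticipated toxicities from general morbidity. Under Table 6 the any-AESI line also counts every respiratory event in patients with chronic lung disease who are using a nebulised drug. Protocol 5.3 anticipates "local respiratory events such as, but not limited to, dysphonia, oropharyngeal pain, and cough while taking LAI". Wherever such terms code to the respiratory SOC, they become AESIs. The AESI tables for withdrawal, interruption, severity and relatedness use the same definition.

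For an inhaled aminoglycoside, a reader will want the number of subjects with any ototoxicity event and with any nephrotoxicity event. The SAP text does not ask for either. SAP 6.1 treats analyses outside the plan as post hoc, so group counts added later risk that label.

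**Working it through.** The plan states no AESI rate and has no sample-size calculation, so there is no figure to reproduce. The check is mainly structural.

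**1. Coverage of the respiratory SOC.** A respiratory preferred term is either named in one of the Table 6 groups or is not. If it is named, it is an AESI. If it is not, Other Respiratory makes it one. Every respiratory term is therefore an AESI. Three consequences need no assumed rate:

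- The respiratory block of table 14.3.6.2 (treatment-emergent AESIs) equals that of 14.3.1.2 (all TEAEs).
- Duration table 14.3.6.10 repeats 14.3.1.10, since both are confined to the respiratory SOC.
- P(any AESI) ≥ P(any respiratory-SOC TEAE).

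Six of the nine groups contain respiratory terms, so the respiratory SOC row cannot separate alveolitis, bronchospasm or haemoptysis from the catch-all. Only the preferred-term rows can.

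**2. How far the any-AESI line could move (assumed rates).** Let a be the proportion of subjects with an AESI in the six protocol categories and b the proportion with an Other Respiratory event. Under independence, any-AESI = 1 − (1 − a)(1 − b). Without independence it lies between max(a, b) and min(1, a + b). The two exacerbation groups are left out, and including them could only raise the figure.

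| a | b | any-AESI, independent | bounds | share of AESI subjects with no protocol-listed AESI |
|---|---|---|---|---|
| 10% | 30% | 37% | 30–40% | 73% |
| 10% | 90% | 91% | 90–100% | 89% |
| 30% | 50% | 65% | 50–80% | 54% |
| 40% | 30% | 58% | 40–70% | 31% |
| 40% | 90% | 94% | 90–100% | 57% |

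The last column is 1 − a/(any-AESI). For a = 30% and b = 50%, any-AESI = 1 − 0.70 × 0.50 = 0.65 and the share is 1 − 0.30/0.65 = 54%. Over a = 10–40% and b = 30–90%, the reported figure runs from 37% to 94%. Only the direction is informative.

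**3. Recovering group counts from SOC and term rows.** Counts from Table 6:

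- Nephrotoxicity has 16 terms: 8 in Renal and urinary disorders and 8 in Investigations. Bronchospasm also has terms in Investigations.
- Ototoxicity has 11 terms: 7 in Ear and labyrinth disorders and 4 in Nervous system disorders. Neuromuscular also has terms in Nervous system disorders.

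If two SOC rows hold x and y subjects, all from one group, the group total lies between max(x, y) and x + y. With hypothetical rows of 15 and 12 among the roughly 200 subjects expected (protocol 3.6.1), the total is 15 to 27, or 7.5% to 13.5%. If the larger row is the shared SOC, some of its subjects may belong to the other group and the lower end falls to 12 (6.0%). Term rows do not settle the count, because one subject may have several terms.

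**4. Terms in two groups.** Balance disorder is in both Neuromuscular and Ototoxicity. Both terms of Exacerbation of COPD are also in Infective Exacerbation of Underlying Disease. No counting rule is given.

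**The case against.** A reader might infer that no count of subjects with ototoxicity or nephrotoxicity will be produced. The documents do not support that. Overall AESI summaries 14.3.6.1 and 14.3.7.1 are planned with rows not described, the mock-ups are elsewhere, and Table 6 does define groups. What can be said is that the SAP text specifies no such count. These toxicities would not be hidden either: preferred-term counts, hearing loss by CTC grade (9.7), chemistry shift tables (9.5) and a subject-level AESI listing (16.2.23.7) are all planned. But test results are not adverse event group counts, and a hand count from a listing is not a specified analysis.

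A reader might also infer that the AESI signal is swamped. That is a forecast from rates the documents do not give. The effect falls on the any-AESI line and the respiratory SOC row. The ear, renal, nervous-system and musculoskeletal rows are untouched.

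Four further points are fair:

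- Broad respiratory capture is a defensible safety choice for an inhaled drug, and protocol 8.3 does discuss cough and exacerbation within its AESI section. This argues for keeping those summaries, though not for merging them into the any-AESI line.
- The six categories already include bronchospasm, and Table 6 puts dyspnoea, wheezing and asthma there. A six-category line would still contain common respiratory events.
- Listing a term in two groups does no harm under SOC and preferred-term rows. It matters only once group rows exist.
- There is no formal hypothesis, so no decision rule depends on the any-AESI figure.

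**Conclusion.** The point holds in a limited form. Two things follow from the text alone. First, Table 6 extends AESIs beyond the six protocol categories to the entire respiratory SOC. The any-AESI frequency then has the rate of any respiratory TEAE as its floor and does not measure what protocol 8.3 defined. Second, SAP 9.1.1, 9.2.1 and 11.1 specify no subject count per AESI group, and such counts for nephrotoxicity and ototoxicity cannot be rebuilt from the specified rows.

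The size of the inflation is unknown. The 37–94% range rests on assumed rates and independence, and shows direction only. The second conclusion is about the SAP text, because the rows of 14.3.6.1 and the mock-ups cannot be seen. The plan should be amended, since a component of the primary endpoint departs from its protocol definition, but the analysis is descriptive and term-level data remain visible.

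**What to change.** In final SAP 9.1.3 and 9.2.1:

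- (a) Make AESI group the top row level of the 14.3.6.x and 14.3.7.x tables. Give the number and percentage of subjects with at least one event per group, overall and by INS-212 arm, with SOC and preferred term beneath.
- (b) Report an any-AESI line limited to the six protocol 8.3 categories. Keep Other Respiratory and the two exacerbation groups, but show them separately.
- (c) State that a term listed in two groups (Balance disorder and the two COPD terms) counts in each group but only once in any total.

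The cost is SAP wording and table shells, with no new data. Nothing is lost: all respiratory terms stay in the TEAE tables, exacerbation and cough have their own items in the overall summary (9.1.1, items 8 to 10), and cough also has tables 14.3.8.1 and 14.3.8.2. The one drawback is that the any-AESI percentage may differ from any earlier table built on the broad list, which a footnote can explain.
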